6.4.2. Additional considerations

The percentage of subjects with at least one grade 3 **local AE** (solicited and unsolicited), with at least one grade 3 **general AE** (solicited and unsolicited) and with any grade 3 AE during the 7-day or 30-day follow-up period after vaccination will be tabulated with exact 95% CI.

Descriptive summary of the number of days with solicited local/general adverse event during the 7 day (Days 1-7) post-vaccination period will be presented.

The percentage of subjects with SAE within 30 days (Day 1-30) after vaccination with its exact 95% CI will be tabulated by group and by MedDRA preferred term. Similar table will be generated for SAE from study start up to Day 90 and from study start up to study end.

SAEs, death, and withdrawal due to AE(s) reported during the entire study will be tabulated.

6.4.2.1. Exclusion of implausible solicited Adverse Event

Some local and systemic adverse events will be directly measured by the subject and will be subject to a reconciliation process, even if they are biologically implausible.

Therefore, these implausible measurements will be removed from the analysis but included in listings. Implausible measurements are summarized in the table below:

Table 3 Implausible Solicited Adverse Events

Parameter	Implausible measurements
Body temperature	$\leq 33^{\circ}\text{C}$ or $\geq 42^{\circ}\text{C}$
Erythema	Measurements < 0 mm For subjects ≥ 6 years: ≥ 900 mm
Swelling	Measurements < 0 mm For subjects ≥ 6 years: ≥ 500 mm

6.4.2.2. Combined Solicited and Unsolicited Adverse Events

A summary of subjects with all combined solicited (regardless of their duration) and unsolicited adverse events will be provided. Solicited adverse events will be coded by MedDRA as per the following codes

Solicited symptom	Lower level term code	Corresponding Lower level term decode
Pain	Injection site pain	10022086
Redness	Redness at injection site	10022098
Swelling	Swelling at injection site	10053425
Fatigue	Fatigue	10016256
Fever	Fever	10016558
Headache	Headache	10019211
Gastrointestinal symptoms	Gastrointestinal disorder	10017944

Please note – to check for AE term in cDISC during dry run

For clinicaltrials.gov and EudraCT posting purposes, a summary of combined solicited and unsolicited non-serious adverse events will be produced by System Organ Class and preferred terms and according to occurrence of each event.

7. ANALYSIS INTERPRETATION

All comparative analyses will be descriptive with the aim to characterise the difference in immunogenicity between groups. These descriptive analyses should be interpreted with caution considering that there is no adjustment for multiplicity for most of these comparisons.

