1.5.4. Rationale for the use of placebo

The placebo group is included as a control for both the safety/reactogenicity and the immunogenicity assessments.

[figure not shown]

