10.10. Interpretation of analyses

All comparative analyses will be descriptive with the aim to characterise the difference in reactogenicity/immunogenicity between groups. These descriptive analyses should be interpreted with caution considering that there is no adjustment for multiplicity for these comparisons.

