3. OBJECTIVES

3.1. Primary objective

- To evaluate the safety and reactogenicity of three dose levels (30, 60, 120 µg) of the RSV maternal investigational vaccine administered as a single intramuscular injection, as compared to placebo up to 1-month post vaccination (Day 31).

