4. ENDPOINTS

4.1. Primary endpoints

- Occurrence of any adverse events (AEs) from vaccination during a 30-day follow up period, for all subjects in all groups:
 - Occurrence of each solicited local and general symptom during a 7-day follow-up period;
 - Occurrence of any unsolicited AE during a 30-day follow up period;
 - Occurrence of Serious AEs during a 30-day follow up period;
 - Occurrence of any haematological (Leukocytes, Neutrophils, Lymphocytes, Eosinophils, Haemoglobin, Platelets) and biochemical (alanine aminotransferase [ALT], aspartate aminotransferase [AST], creatinine, blood urea nitrogen [BUN]) laboratory abnormalities at Day 8 and Day 31.

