6.4.1.1. Within group analysis

The percentage of subjects with at least one **local AE** (solicited and unsolicited), with at least one **general AE** (solicited and unsolicited) and with any AE during the 7-day or 30-day follow-up period after vaccination will be tabulated with exact 95% CI. The same computations will be done for any \geq Grade 2 AEs, for any AEs considered related to vaccination, for any Grade 3 AEs considered related to vaccination and for AEs resulting in medically attended visit.

The percentage of subjects reporting each individual **solicited local AE** (any, each grade, resulting in medically attended visit) during the 7-day follow-up period after vaccination will also be tabulated based on maximum intensity per subject for each study vaccine group. The percentage of subjects reporting each individual **solicited general AE** (any, each grade, any related, any Grade 2 related, any Grade 3 related, resulting in medically attended visit) during the 7-day follow-up period after vaccination will also be based on maximum intensity per subject for each study vaccine group.

For fever during the 7-day follow-up period after vaccination, the number and percentage of subjects reporting any fever and fever by half degree ($^{\circ}\text{C}$) cumulative increments will be reported. Similar tabulations will be performed for causally related fever, Grade 3 causally related fever and fever resulting in a medically attended visit. In addition, the prevalence of any and Grade 3 fever will be presented graphically over time after vaccination.

The percentage of subjects with any **unsolicited** symptoms within 30 days after vaccination with its exact 95% CI will be tabulated by group and by MedDRA System Organ Class and preferred term. Similar tabulation will be done for Grade 3 unsolicited symptoms, for any causally related unsolicited symptoms, for Grade 3 causally related unsolicited symptoms and for unsolicited symptoms resulting in a medically attended visit (the verbatim reports of unsolicited symptoms will be reviewed by a physician and the signs and symptoms will be coded according to the MedDRA Dictionary for Adverse Reaction Terminology. Every verbatim term will be matched with the appropriate Preferred Term).

SAEs reported throughout the study will be described in detail.

Pregnancy exposures throughout the study and pregnancy outcomes will be described in detail (if applicable).

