9. CHANGES FROM PLANNED ANALYSES

None

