All summaries	% of difference, including LL & UL of CI	2
All summaries	p-value	3

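### The primary objective compares safety and reactogenicity with placebo, but neither the protocol nor the SAP defines an estimate of the difference from placebo for any safety endpoint

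*SAP*

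**What the plan says.** **Objective and control.** SAP 3.1 sets the primary objective as safety and reactogenicity of the three dose levels, "as compared to placebo up to 1-month post vaccination (Day 31"). Protocol 2.1 says the same. Protocol 1.5.4 gives the placebo group its purpose: "The placebo group is included as a control for both the safety/reactogenicity and the immunogenicity assessments". The primary endpoints (Protocol 10.1, SAP 4.1) are occurrences: "Occurrence of any adverse events (AEs) from vaccination during a 30-day follow up period, for all subjects in all groups". They name no between-group measure.

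**Safety analysis.** The only analysis subsection carried from the protocol into SAP 6.4.1 is "6.4.1.1. Within group analysis", and SAP 6.4.2 adds further per-group summaries. Protocol 10.8 likewise has a single subsection, on within-group assessment. No safety template (15 to 34) has a column for a difference or ratio against placebo. Templates 16, 17, 20 and 23 give n, % and an exact 95% CI per group. Laboratory Templates 26 to 28 give n and % only.

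**Interpretation.** Protocol 10.10 describes the comparative analyses as descriptive, "with the aim to characterise the difference in reactogenicity/immunogenicity between groups". The matching SAP sentence is "All comparative analyses will be descriptive with the aim to characterise the difference in immunogenicity between groups". SAP Section 9 records no changes from planned analyses.

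**Display rule.** SAP 11.2.5 sets two decimals for a percentage "of difference, including LL" and UL of its CI, but no safety analysis or template produces such a quantity.

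**The concern.** The primary objective is comparative, and placebo is in the trial partly to serve it. The quantity that answers it most directly is the excess of each reaction over saline, with its uncertainty. The plan leaves the reader to form that from separate per-group figures.

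The secondary immunogenicity objective is also worded as a comparison with placebo (SAP 3.2). For it, SAP 6.3.1.2 and Template 49 supply dose-to-placebo ratios, confidence intervals and Dunnett-adjusted p-values. Those comparisons are exploratory too, so a descriptive design does not explain why the primary objective has no contrast at all.

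At stake is how clearly the first-in-human safety result can be read. Two 95% intervals side by side invite a check for overlap, which understates the evidence for a moderate excess over placebo. For laboratory abnormalities, a named primary endpoint, even the per-group intervals are absent.

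**Working it through.** **1. The plan's own safety figures (Protocol 10.4), n = 125 per group.**
- Upper exact 95% limit with zero events: 1 − 0.025^(1/125) = 2.91% (stated 2.9%).
- Probability of at least one event: 1 − 0.987^125 = 80.5% at a 1.3% rate (stated 80%), and 1 − 0.982^125 = 89.7% at a 1.8% rate (stated 90%).

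All reproduce. All are single-group figures, and none concerns a difference from placebo.

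**2. Inputs for the comparison.** The 125 per group and 1:1:1:1 allocation are from Protocol 5.2.2.2.1. The per-group interval is Clopper-Pearson (SAP 11.1). The documents give no expected adverse event rates, so every rate and count below is an assumption.

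**3. One worked example: 56/125 on vaccine (44.8%), 38/125 on placebo (30.4%).**
- Clopper-Pearson intervals: 35.9 to 54.0% and 22.5 to 39.3%. They overlap.
- Newcombe interval for the difference d = p1 − p0: lower = d − √[(p1 − l1)² + (u0 − p0)²], upper = d + √[(u1 − p1)² + (p0 − l0)²], where l and u are Wilson limits.
- Wilson limits: 36.37 to 53.54% and 23.02 to 38.95%.
- Lower: 14.4 − √(8.43² + 8.55²) = 14.4 − 12.0 = 2.4 points.
- Upper: 14.4 + √(8.74² + 7.38²) = 14.4 + 11.4 = 25.8 points.

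The difference is 14.4 points (2.4 to 25.8), which excludes zero although the separate intervals overlap. The same happens at 25/125 against 13/125: intervals 13.4 to 28.1% and 5.7 to 17.1%, difference 9.6 points (0.6 to 18.5).

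**4. How often this matters.** For each pair of true rates, sum the product of the two binomial probabilities over all pairs of counts from 0 to 125 that meet the condition.

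| True rates (assumed) | Exact intervals do not overlap | Newcombe CI excludes zero |
|---|---|---|
| 45% vs 30% | 33% | 69% |
| 20% vs 10% | 23% | 60% |
| 25% vs 10% | 59% | 89% |
| 40% vs 20% | 72% | 94% |
| 50% vs 20% | 98.6% | 99.9% |
| 40% vs 10% | 99.8% | 100% |
| Equal, 10% to 45% | 0.3 to 0.4% | 4.6 to 5.0% |
| Equal, 2% | not tabulated | 2.3% |
| Equal, 1% | not tabulated | 0.5% |

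The loss from informal reading is large for moderate differences and almost nil for large ones. For rare events the Newcombe interval is itself conservative.

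**5. Number of intervals the fix adds.** Seven solicited events × 2 levels (any, Grade 3) = 14. Any unsolicited AE, any Grade 3 AE, any related AE and Grade 2 or higher laboratory abnormality add 4. 18 × 3 doses = 54. With no true effect, at most about 54 × 0.05 = 2.7 would exclude zero by chance.

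**The case against.** The strongest reply is that this is a phase 1/2 trial with no safety hypothesis. Its endpoints are occurrences by group, and the main tables show each dose beside placebo with exact intervals. Any reader can compute a difference and its interval from the printed n and N. This stands against one tempting inference, that nothing in the plan answers the primary objective. The tables do support a descriptive comparison. What is missing is a planned estimate of the excess and its uncertainty.

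A reader might also infer that the SAP removed a planned safety comparison. The documents do not support that. Protocol 10.8 specifies only within-group assessment, and the one between-groups section (Protocol 10.9.2) covers antibodies. The SAP dropped a stated aim, not a specified analysis, so recording no change in SAP Section 9 can be defended on a narrow reading. The protocol still announces a reactogenicity comparison that neither document carries out.

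Third, neither document tells anyone to compare groups by interval overlap. That is correct. The detection rates above describe an informal habit the layout invites, at rates chosen for illustration, and for large excesses the habit costs almost nothing.

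Finally, the decimals row in SAP 11.2.5 sits in a standard annex and applies to all summaries. It may be generic formatting, so it is weak evidence that a safety difference was intended.

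**Conclusion.** The point holds as a gap in estimation. The objective is relative to placebo, the protocol states an aim of describing differences in reactogenicity, and no safety analysis or template in either document estimates such a difference. The SAP narrows the stated aim without saying so. The gap begins in the protocol.

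Its size depends on the true rates, which the documents do not give. For assumed moderate excesses at 125 per group, separate intervals reveal the difference roughly one third to one half as often as an interval for the difference (23% against 60%, 33% against 69%). For a 30-point excess over 20% there is practically no loss. No figure stated in the plan is wrong on this account, and neither the data collected nor the sample size needs to change. It is an inexpensive improvement, not a flaw that prevents the trial from describing its safety results.

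**What to change.** 1. Restore *reactogenicity* in the SAP Section 7 sentence so that it agrees with Protocol 10.10.
2. Add one descriptive table to SAP 6.4.2 and Annex 3: risk difference, each RSV dose minus placebo, with a two-sided 95% score-type CI (Miettinen-Nurminen or Newcombe). Rows: each solicited AE (any, Grade 3), any unsolicited AE, any Grade 3 AE, any related AE, and Grade 2 or higher laboratory abnormality. For adverse events use the denominators already set in SAP 11.2.4.
3. Label the table descriptive and unadjusted for multiplicity. No hypothesis test is needed.

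The cost is one table shell and standard code on data already collected. The drawback is 54 unadjusted intervals, of which two or three could exclude zero by chance, so the caution in Protocol 10.10 and SAP Section 7 should be printed with the table.

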8. CONDUCT OF ANALYSES

8.1. Sequence of analyses

In order to obtain early immunogenicity data of the different formulations of the investigational RSV Maternal vaccine, an interim analysis will be performed on Exposed Set when immunogenicity data up to Day 31 for the Step 1 subjects becomes available. This analysis will be performed on Exposed Set on data as available (i.e partially clean or non-clean data). The templates and listings to be reported for this analysis will be detailed in TFL TOC of this SAP.

To ensure the study team remains blinded, the analysis will be performed by an unblinded statistician outside GSK and the iSRC will act as a firewall team, to review the aggregated summaries for risk of unblinding of individual subjects, before these are released to the team. For this analysis only a statistical report will be prepared

The final statistical analyses will be performed in 2 steps:

- A first analysis will be performed when all safety and immunogenicity data up to at least Day 91 is available in all subjects. At this point, the study statistician will be unblinded (i.e. will have access to the individual subject treatment assignments), but no individual listings will be provided to investigators until the final study report. However, summary results may lead to the unblinding of some specific subjects in case an event occurred only in one group; steps will be taken to minimize this risk.
- The final analysis covering all primary and secondary endpoints as well as any evaluated tertiary endpoint(s) will be performed when all data up to study conclusion are available. A clinical study report will only be written at this stage and individual listings will be provided as part of it.

If the data for tertiary endpoints becomes available at a later stage, (an) additional analysis/analyses will be performed. These data will be documented in annex(es) to the study report and will be made available to the investigators at that time

Description	Analysis ID	Disclosure Purpose (CTRS=public posting, SR=study report, internal)	Dry run review needed (Y/N)	Study Headline Summary (SHS)requiring expedited communication to upper management (Yes/No)	Reference for TFL
Final - Up to Day 181	E1_01	CTRS, Study report	Y	Y	See sheet TOC-DAY181 in TFL TOC
D31-Step 1	E1_02	Internal	Y	Y	See sheet TOC-S1-D31 in TFL TOC
Up to Day 91	E1_03	CTRS	Y	Y	See sheet TOC-DAY91 in TFL TOC

8.2. Statistical considerations for interim analyses

All analyses are descriptive. Therefore, the conduct of interim analyses has no impact on interpretation of study results.

9. CHANGES FROM PLANNED ANALYSES

None

10. LIST OF FINAL REPORT TABLES, LISTINGS AND FIGURES

The TFL TOC provides the list of tables/listings and figures needed for the study report. It also identifies the tables eligible for each analyses and their role (synopsis, in-text, post-text, SHS, CTRS,...). Note that all TFL aimed to be included as post-text are noted as post-text even if these are tabulation of individual data such as listing of SAE. The post-text material contains all source material for the study report and accordingly a post-text table may be redundant with an in-text table.

The following group names will be used in the TFLs, to be in line with the T-domains:

Group order in tables	Group label in tables	Group definition for footnote
1	RSV MAT 30	Subject receiving RSVPreF3 low dose
2	RSV MAT 60	Subject receiving RSVPreF3 mid dose
3	RSV MAT 120	Subject receiving RSVPreF3 high dose
4	Placebo	Subject receiving placebo

The following sub-group names will be used in the TFLs

Sub-group order in tables	Sub-group label in tables	Sub-group definition for footnote
1	18-32Y	Subjects 18-32 years of age
2	33-45Y	Subjects 33-45 years of age

11. ANNEX 1 STANDARD DATA DERIVATION RULE AND STATISTICAL METHODS

11.1. Statistical Method References

The exact two-sided 95% CIs for a proportion within a group will be the Clopper-Pearson exact CI [Clopper CJ, Pearson ES. The use of confidence or fiducial limits illustrated in the case of binomial. *Biometrika*. 1934;26:404-413].

11.2. Standard data derivation

11.2.1. Date derivation

- SAS date derived from a character date: In case day is missing, 15 is used. In case day & month are missing, 30June of the year will be used.
- Onset day for an event (AE, medication, etc.): The onset day is the number of days between the study vaccination and the onset/start date of the event. This is 1 for an event starting on the same day as a vaccination. See SAS date derived in case the start date of the event is incomplete.
- Duration: Duration of an event is expressed in days. It is the number of days between the start & the stop dates + 1. Therefore, duration is 1 day for an event starting & ending on the same day.

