While pregnancy itself is not considered an AE or SAE, any adverse pregnancy outcome or complication or elective termination of a pregnancy for medical reasons will be recorded and reported as an AE or a SAE.

Note: The pregnancy itself should always be recorded on an electronic pregnancy report.

The following should always be considered as SAE and will be reported as described in Sections 8.4.1 and 8.4.3:

- Spontaneous pregnancy loss, including:
 - spontaneous abortion, (spontaneous pregnancy loss before/at 22 weeks of gestation)
 - ectopic and molar pregnancy
 - stillbirth (intrauterine death of foetus after 22 weeks of gestation).
- Any early neonatal death (i.e. death of a live born infant occurring within the first 7 days of life).
- Any congenital anomaly or birth defect (as per [CDC MACDP] guidelines) identified in the offspring of a study subject (either during pregnancy, at birth or later) regardless of whether the foetus is delivered dead or alive. This includes anomalies identified by prenatal ultrasound, amniocentesis or examination of the products of conception after elective or spontaneous abortion.

Furthermore, any SAE occurring as a result of a post-study pregnancy AND considered by the investigator to be reasonably related to the investigational vaccines will be reported to GSK as described in Section 8.4.3. While the investigator is not obligated to actively seek this information from former study participants, he/she may learn of a pregnancy through spontaneous reporting.

8.3. Detecting and recording adverse events, serious adverse events and pregnancies**8.3.1. Time period for detecting and recording adverse events, serious adverse events and pregnancies**

All AEs starting within 30 days following administration of the study vaccine (Day 1 to Day 30) must be recorded into the appropriate section of the eCRF, irrespective of intensity or whether or not they are considered vaccination-related.

The time period for collecting and recording SAEs will begin at the receipt of the study vaccine and will end at the contact at Day 181. See Section [8.4](#) for instructions on reporting of SAEs.

All AEs/SAEs leading to withdrawal from the study will be collected and recorded from the time of the receipt of the study vaccine.

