Appendix Table I.J - Reason for non-eligibility

Appendix Table II.Ai - Solicited local adverse events

Appendix Table II.B - Solicited general adverse events

Appendix Table II.Ci - Unsolicited adverse events within (30) days post-vaccination

Appendix Table II.Cii - Unsolicited adverse events after (30) days post-vaccination

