Related* = any grade >0 for Fatigue, Gastrointestinal symptoms, Headache and any $\geq 38.0^{\circ}\text{C}$ for Temperature considered related to vaccination by the investigator

Please note – to check for AE term in cDISC during dry run

Template 21 Number of days with solicited general adverse event during the 7-day (Days 1-7) post-vaccination period <Exposed Set>

		<Each group>	
Symptom	Statistic	value	value
Fatigue	n	xxxx	xxxx
	Mean	xx.x	xx.x
	Minimum	xx.x	xx.x
	Q1	xx.x	xx.x
	Median	xx.x	xx.x
	Q3	xx.x	xx.x
	Maximum	xx.x	xx.x
Gastrointestinal symptoms	n	xxxx	xxxx
	Mean	xx.x	xx.x
	Minimum	xx.x	xx.x
	Q1	xx.x	xx.x
	Median	xx.x	xx.x
	Q3	xx.x	xx.x
	Maximum	xx.x	xx.x
Headache	n	xxxx	xxxx
	Mean	xx.x	xx.x
	Minimum	xx.x	xx.x
	Q1	xx.x	xx.x
	Median	xx.x	xx.x
	Q3	xx.x	xx.x
	Maximum	xx.x	xx.x
Temperature (Oral) ($^{\circ}\text{C}$)	n	xxxx	xxxx
	Mean	xx.x	xx.x
	Minimum	xx.x	xx.x
	Q1	xx.x	xx.x
	Median	xx.x	xx.x
	Q3	xx.x	xx.x
	Maximum	xx.x	xx.x

<each group>:

RSV MAT 30 = Subject receiving RSVPreF3 low dose

RSV MAT 60 = Subject receiving RSVPreF3 mid dose

RSV MAT 120 = Subject receiving RSVPreF3 high dose

Placebo = Subject receiving placebo

[figure not shown]
n = number of doses with the symptom

Q1 = 25th percentile

Q3 = 75th percentile

Please note – to check for AE term in cDISC during dry run

Template 22 Percentage of subjects reporting fever (any and grade 3) and other solicited general adverse events (any grade /grade 2,3/ grade 3) during the 7-day (Days 1-7) post-vaccination period by maximum intensity <Exposed set>

RSV MAT 30 = Subject receiving RSVPreF3 low dose

RSV MAT 60 = Subject receiving RSVPreF3 mid dose

RSV MAT 120 = Subject receiving RSVPreF3 high dose

Placebo = Subject receiving placebo

Grade 3 fever = Temperature >39.0 °C

Please note – to check for AE term in cDISC during dry run

Template 23 Percentage of subjects reporting the occurrence of <any, grade 3> <unsolicited symptoms, serious adverse events> classified by MedDRA Primary System Organ Class and Preferred Term <with causal relationship to vaccination, with medically attended visit>, within the 30-day (Days 1-30) post-vaccination period <Exposed Set>

Primary System Organ Class (CODE)	Preferred Term (CODE)	Each group N =			
		n*	n	%	95% CI
LL	UL				
At least one symptom					
Gastrointestinal disorders (10017947)	Diarrhoea (10012735) Teething (10043183) Vomiting (10047700)				
General disorders and administration site conditions (10018065)	Pyrexia (10037660)				

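### A missing AE start day is set to the 15th with no floor at vaccination, so some post-vaccination AEs get an onset day below 1 and could miss the Day 1-30 tables

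*SAP*

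**What the plan says.** SAP 11.2.1 gives the partial-date rule: "SAS date derived from a character date: In case day is missing, 15 is used". If day and month are both missing, 30 June is used. The same section defines onset day so that an event starting on the day of vaccination has onset day 1, and it sends incomplete start dates to the imputation rule: "See SAS date derived in case the start date of the event is incomplete". Duration is stop date minus start date plus 1, so it uses the same start date.

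Onset timing matters in these places:

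- SAP 6.4.1.1 tabulates unsolicited "symptoms within 30 days after vaccination with its exact 95% CI will be tabulated by group", and Template 23 in SAP 13.2 is titled for events "within the 30-day (Days 1-30) post-vaccination period <Exposed Set>".
- SAP 13.1 plans two listings, "Unsolicited adverse events within (30) days post-vaccination" and "Unsolicited adverse events after (30) days post-vaccination".
- Template 32, the SAE listing, has columns for day of onset and duration.

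On collection, Protocol 8.3.1 states: "All AEs starting within 30 days following administration of the study vaccine (Day 1 to Day 30) must be recorded". Protocol 8.1.1 assigns conditions present before vaccination to medical history. Footnote 7 to Protocol Table 4 limits pre-vaccination recording to SAEs related to study participation.

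**The concern.** A mid-month default ignores the one thing known about these records. With the narrow exception of study-related SAEs before vaccination, an AE in the database started on or after the vaccination date. Where vaccination falls in the second half of a month, the rule puts the start of a same-month AE before the injection, which the protocol's collection rules exclude.

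The number itself is wrong wherever it is displayed, as in the SAE listing. If tables and listings select on derived onset day, the record also disappears. It fails the Day 1-30 condition, and it fits neither the listing for events within 30 days nor the listing for events after 30 days. Unsolicited AEs over 30 days are a component of the primary endpoint (SAP 4.1) in a first-in-human trial. Solicited symptoms and laboratory abnormalities are not affected.

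**Working it through.** **Inputs.** Missing day is set to 15; onset day is 1 for a same-day event; the imputed date feeds the onset day (all SAP 11.2.1). The AE window is Day 1 to Day 30 (Protocol 8.3.1).

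**Formula.** Onset day = start date - vaccination date + 1. For a same-day event this gives 0 + 1 = 1, the SAP's own value.

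**Threshold.** For a day-missing AE in the vaccination month, onset day = 15 - v + 1 = 16 - v, where v is the calendar day of vaccination.

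| v | Onset day |
|---|---|
| 14 | 2 |
| 15 | 1 |
| 16 | 0 |
| 20 | -4 |
| 30 | -14 |
| 31 | -15 |

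The cut-off is the 16th. It stays there if the scale has no Day 0, since the 16th then gives -1. In a 365-day year 185 dates fall on the 16th or later (185/365 = 50.7%).

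**How often.** Assume vaccination dates uniform over a year and true onset uniform over the window. For each of the 365 vaccination dates and each true onset day, set the start to the 15th of the true onset month and recompute the onset day.

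| True onset | Pairs | Imputed below Day 1 |
|---|---|---|
| Day 1-30 | 10,950 | 1,523 (13.9%) |
| Day 1-7 | 2,555 | 1,043 (40.8%) |
| Day 8-30 | 8,395 | 480 (5.7%) |

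Of the Day 1-30 pairs, a further 1,260 (11.5%) land above Day 30, and 74.6% stay in the window. In the other direction, 1,516 of 5,475 pairs with true onset Day 31-45 (27.7%) are pulled into Day 1-30. Calendars for 2018 and 2019 give the same percentages.

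**Share of all Day 1-30 unsolicited AEs.** Multiply 13.9% by the share with a missing day, which the documents do not give. At an assumed 1%: 0.139 x 0.01 = 0.14%. At 5%: 0.70%. At 10%: 1.4%.

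**Same enumeration with a floor** (later of the 15th and the vaccination date, applied only when month and year equal those of vaccination):

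- None fall below Day 1, 11.5% remain above Day 30, and the in-window share rises to 88.5%.
- Mean absolute error in onset day falls from 7.6 to 6.8 days.
- The 1,523 floored pairs move to Day 1, on average 4.8 days (at most 15) before true onset. All have true onset on Days 1-16.
- None of the 55,115 pairs (365 x 151) with true onset Day 31-181 is moved.

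**Why the floor should not cover year-only dates.** Flooring the 30 June rule at vaccination would move 11,929 of those 55,115 pairs (21.6%) to Day 1. Among July-December vaccinations it would move 11,929 of 27,784 (42.9%).

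**The case against.** The strongest objection is that loss from the tables is not shown. SAP 11.2.1 defines an onset-day variable but does not say that this variable filters the Day 1-30 tables. SAP 10 says "The TFL TOC provides the list of tables/listings and figures needed for the study report", and that list is not among the documents. Some text leans towards selection by what was reported: Protocol 8.3.1 has these AEs entered in a designated part of the eCRF, and SAP 11.2.4 counts as event-free only subjects who did not report the event. This stands, and exclusion is claimed only as a possibility. It does not remove the wrong onset day, which would still appear in Template 32.

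Second, partial dates should be rare. Investigators verify diary cards with the subject (Protocol 5.6.17), omissions may be queried (Protocol 11.1) and monitors verify source data (Protocol 11.2). Moreover, 1,043 of the 1,523 affected pairs (68%) have true onset on Days 1-7, which have their own diary card, collected at Visit 2. If missing days occurred only on the second card, 5.7% of day-missing AEs would be affected; at assumed missing shares of 1%, 5% or 10% of those AEs, that is about 0.06%, 0.29% or 0.57%. This also stands, so the range of 0.14% to 1.4% may be on the high side.

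Third, a mid-month default is only an approximation, and SAP 11.2.2 openly accepts similar inconsistencies for partial birth dates. But birth dates carry no known bound of this kind, whereas AE dates do.

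Fourth, the floor is a partial cure and the analyses are descriptive. Both are true, and both keep the point minor.

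**Conclusion.** The concern holds, as a minor point. The SAP's stated rule gives an onset day below 1 to every day-missing AE in the vaccination month when vaccination is on the 16th or later. This follows from the text and needs no assumption. The 13.9% rests on uniform vaccination dates and uniform onset over Days 1-30; the effect on all Day 1-30 unsolicited AEs also rests on an assumed missing-day share. Loss from the tables and both listings follows only if they select on derived onset day. The rule ignores treatment group, so no between-group bias is claimed.

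**What to change.** Add to SAP 11.2.1: if only the day of an AE start date is missing, and the known month and year equal those of vaccination, use the later of the 15th and the vaccination date, unless a complete stop date before vaccination, or recording as a pre-vaccination SAE related to study participation, shows earlier onset. Do not extend this floor to dates with day and month both missing.

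Also state whether the Day 1-30 tables and the two unsolicited AE listings select by derived onset day or by collection period. If by collection period, table and listing membership is settled and the floor only corrects the displayed onset day and duration.

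The cost is one SAP sentence with one line of derivation code, plus the statement of the selection basis. The downside is that floored events are all placed on Day 1, somewhat earlier than they truly began. Day-missing AEs shifted past Day 30, later AEs pulled into the window, and year-only dates remain as they are.
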